
At present there is no scientific evidence in dentistry about the origin and treatment of perimplatitis and mucositis. These peri-implant pathologies can be partially prevented through periodontal diagnosis, correct implant placement and prosthetic loading.

In the literature, there is a physiological bone loss around implant after the placement (1 mm the first year and 0.2 mm each subsequent year). Different types of implants have been designed (laserization of the collar, platform switching..) to try to control this phenomenon with discordant results. Different surgical protocols for implant insertion have been created to minimize bone resorption: a subcrestal implant seems to partially overcome this problem even if this procedure increase the transmucosal tunnel: growing the risk of peri-implant soft tissue infection.

Tissue healing around the implants is not comparable to the natural dental element: the risk of inflammation and consequently of infection is higher around the implants because there is no stable seal between the two structures (tissue and implant).

The prosthetic structure of the GFA was created to overcome these problems: crestal bone reabsorption and transmucosal tunnel. Our objective is to validate or deny this claim.

STUDY OUTCOMES

- a. Primary outcome measure: radiographically change in MBL
- b. Secondary outcomes changes in the following clinical parameters:
 - PD (Probing Depth),
 - REC (Clinical Gingival Recession),
 - BOP (Bleeding on Probing),
 - PI (Plaque Index).

STUDY POPULATION

Forty (40) adults, aged 18-75 years, will be entered into study (randomized). It is expected that forty (34) subjects will complete the study.

Randomized subjects who deviate from the protocol (major protocol deviation) and, for this reason, are excluded from the analysis, will be replaced to guarantee that the sample required for the analysis (34) is reached.

Patients will be treated at the Department of Surgical Specialties Radiological Science and Public Health, School of Dentistry, Section of Periodontics, Brescia, Italy from 09/2020.

Inclusion Characteristics

- Comprehension and signed Informed Consent Form.
- Male and female subjects, aged 18-75 years, inclusive.
- Good general health (free of systemic diseases such as diabetes, HIV infection or genetic disorder, ongoing malignant disease of any type that could influence the outcome of the treatment and might interfere with the evaluation of the study objectives).

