 - a. Prosthetic finalization and loading.
 - b. Periodontal charting around the new prosthetic crown (PD, BOP, PI, REC).
 - c. Take a standardized x- Ray (Bite Block).
- 6. Visit 5 (6 months from baseline – T1): (Follow-up)
 - a. Control.
 - b. Periodontal charting around the prosthetic crown (PD, BOP, PI, REC).
 - c. Take a standardized x- Ray (Bite Block).
 - d. Professional dental hygiene session.
- 7. Visit 6 (12 months from baseline – T2):
 - a. Control.
 - b. Periodontal charting around the prosthetic crown (PD, BOP, PI ,REC).
 - c. Take a standardized x- Ray (Bite Block).
 - d. Professional dental hygiene session.
- g. All treatments are made by the same clinician;
- h. Data collection:
 - Standardized X- Ray: control periapical radiographs is performed using a long-cone paralleling technique and an individual X-ray holder (bite block) to ensure reproducibility. Built thanks to impression material.
 - A calibrated periodontal probe (Click-Probe™ Kerr Dental) is used on six sites per tooth (mesio-buccal, buccal, disto-buccal, mesio-lingual, lingual and disto-lingual) with a standard probing force by the same clinician. Measurements are rounded to the nearest millimeter;

- j. Clinical and radiographical assessment data will be recorded via hard copy CRFs. CRFs will be submitted to a data entry staff member for entry into the statistical database. At the conclusion of the study, such statistical database will be submitted to the statistician for the preparation of the statistical analysis and the final study report.
- k. Prosthetic finalization is given to the dental laboratory.

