3. PROCEDURE

Screening and Selection of Subjects

Patients visiting the U.O. Odontostomatology of ASST Spedali Civili of Brescia will be asked to participate in this study. Subjects will report to the clinical facility and be screened by the dental examiner to identify those subjects who meet the inclusion/exclusion characteristics. The findings of this initial screening procedure will be recorded on the CRF. Subjects who meet the inclusion/exclusion characteristics and sign an Informed Consent Form will be entered into the study.

Baseline Oral Soft and Hard Tissue Assessment

All subjects will receive an evaluation of their oral soft and hard tissues. This examination will include an evaluation of the soft and hard palate, gingival mucosa, buccal mucosa, mucogingival fold areas, tongue, sublingual and submandibular areas and the tonsillar and pharyngeal areas. The results of this evaluation will be recorded on the CRF.

CBCT

All patients receiving a CBCT to confirm the eligibility of each subject and to plan the surgery at Complex Operative Unit of Diagnostic Radiology 2.

Treatment

Patients who have been identified for treatment receive an implant placement and prosthetic finalization will be randomized according to a randomization table generated.

Clinical Periodontal Evaluation

All patients receiving treatment will be evaluated by the dental examiner for the following assessments (see Study Flow Chart):

- Full Mouth Plaque Score (PI);
- Periodontal Inflammation (BOP);
- Probing Pocket Depth (PD);
- Recession (REC);

All parameters will be recorded in the CRF.

Radiographically Evaluation

All patients receiving control reproducible periapical radiographs for evaluation of MBL (mesial and distal) (see Study Flow Chart)

All parameters will be recorded in the CRF.

Follow up

Following completion implant placement and prosthetic finalization, the study start. Radiographically and clinical evaluation will be done at baseline (T0), 6 and 12 months (T1 and T2) in the test and control site. At 6 and 12 months a dental hygiene session and OHI will be done.

Study Flow Chart

Study phase	Enrolment	Treatment	Treatment	Treatment	Follow-up	Follow-up
Study visit	Visit 1	Visit 2	Visit 3	Visit 4 (T0)	Visit 5 (T1)	Visit 6 (T2)
Study Time	- X days	0	3 months	3 months and 1 week	6 months from visit 4	12 months from visit 4
Selection criteria	+					
Informed consent	+					
Demographics, ethnics	+					
General health status	+	+	+	+	+	+

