4. STATISTICAL ANALYSIS

Sample size determination

Sample size was compute assuming a two parallel groups design with balanced groups and an independent sample t-test. We assumed a single implant and a single measurement for patient, a standard deviation of 0.5 mm and an average difference of at least 0.5mm. A total sample size of 34 patients will provide a power of at least 80% at a 5% significance level. Assuming a 15% drop-out , the total sample size will be N=40 patients.

Statistical Analysis

Data will be described using standard statistics such as, mean, median standard deviation and IQR for quantitative variable, and counts and percentages for qualitative variables.

Variation in MBL will be modelled using both a simple t-test for independent samples (after averaging values within patients) as well as a multilevel model using GEE (Generalised Estimating Equations) on individual site measurements and accounting for within subject correlation.

Secondary continuous outcomes will be modelled using GEE with ad hoc error distribution according to outcome (Gaussian for PPD, CAL, REC, binomial for BOP).

Results will be expressed as estimates and relative 95% confidence intervals. A significant level of 5% will be used for all the comparisons and all analysis will be performed using R (version 3.6.3 or higher).

Evaluation of Safety

The following safety variables will be used for the evaluation of safety:

- Adverse events (AE);
- Adverse reactions (AR).

The total number of AEs and the total number of AEs at least possibly related to the study treatment, as well as the total number of patients affected by at least one adverse event will be calculated per treatment group.

The type of AE classified by organ system (according to MedDRA terminology) will be tabulated. Serious and/or unanticipated adverse events and AEs resulting in discontinuation or reduction/withdrawal of the study treatment will be presented separately.

Safety analysis set

Safety summaries will be based on the safety analysis set which will consist of all patients who received the test/control treatment.

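### Primary MBL change is tested by both a t-test and a GEE, with no deciding analysis or visit named and no small-sample method given for the GEE

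*Combined protocol and SAP*

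**What the plan says.** The Study Outcomes section defines the primary endpoint as "Primary outcome measure: radiographically change in MBL" and attaches no time point. Section 3 (Follow up) sets three assessments: "Radiographically and clinical evaluation will be done at baseline (T0), 6 and 12 months (T1 and T2". Section 2 has MBL read at two sites per implant, mesial and distal.

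Section 4 models the change in MBL "using both a simple t-test for independent samples (after averaging values within patients) as well as a multilevel model using GEE". The GEE is fitted to the individual site values and allows for within-patient correlation. The same section adds "A significant level of 5% will be used for all the comparisons". For the remaining endpoints it says "Secondary continuous outcomes will be modelled using GEE with ad hoc error distribution according to outcome"; the periodontal probe behind these data "is used on six sites per tooth" (section 1).

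The sample size was computed for an independent-samples t-test with one measurement per patient, assuming "a standard deviation of 0.5 mm and an average difference of at least 0.5mm". It concludes "A total sample size of 34 patients will provide a power of at least 80% at a 5% significance level", raised to 40 for 15% drop-out.

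No section ranks the two MBL analyses or says what follows if they disagree. For the GEE, no working correlation, variance estimator, reference distribution or small-sample correction is stated; the only software detail is R, version 3.6.3 or higher.

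**The concern.** Two unranked tests of one primary endpoint, each at 5%, leave the primary result to be settled after the data are seen. A difference that is significant by GEE but not by t-test, or at one visit but not the other, could be reported as the trial's finding, and nothing in the plan would contradict it.

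The two methods are also not equally reliable at this size. The ordinary GEE sandwich variance is too small when there are few patients, and a normal reference ignores that the variance is estimated. With about 34 patients, both faults narrow the interval. The secondary outcomes are affected too, because the plan analyses them by GEE only.

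**Working it through.** **Inputs from section 4:** SD 0.5 mm, difference 0.5 mm, 34 evaluable patients in balanced arms (17 each), 5% level, 15% drop-out. The plan does not state sidedness; two-sided is assumed, in line with its 95% intervals.

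**Assumed for the GEE, because the plan is silent:** ordinary sandwich variance, normal reference, one change score per site, both sites present, no covariates, equal arms.

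**1. The plan's own figures.** The noncentrality is (0.5/0.5) × √(17/2) = 2.915 on 32 degrees of freedom, with critical value 2.037. Power is 80.7% at 17 per arm and 78.1% at 16, so 17 is the smallest adequate arm. 34/0.85 = 40. Both stated sizes reproduce.

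**2. How the two tests relate.** Under the assumptions above, the GEE estimate equals the difference in patient means. The sandwich divides by n where the t-test divides by n − 1, so its variance is 16/17 of the t-test's and z = t × √(17/16). The GEE therefore rejects when |t| > 1.960 × √(16/17) = 1.901, against 2.037 for the t-test. Exchangeable GEEs fitted to 8,003 simulated null trials matched this relation to rounding error and rejected in 6.5% (Monte Carlo SE 0.28 points).

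**3. Error and interval width.**
- Type I error: 2 × P(t₃₂ > 1.901) = 6.63%, so coverage is 93.4%.
- Other arm sizes: 6.9% at 15 per arm and 6.4% at 20. With unequal arms, 6.7% at 14/20 and 7.1% at 12/22.
- Standard error for the t-test: 0.5 × √(2/17) = 0.1715 mm. Half-width is 2.037 × 0.1715 = 0.349 mm for the t-test and 1.901 × 0.1715 = 0.326 mm for the GEE, a ratio of 0.933.

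**4. How often the methods disagree.** Because 1.901 < 2.037, the GEE rejects whenever the t-test does, so disagreement runs one way only.

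| True difference (SD 0.5 mm) | t-test significant | GEE significant | GEE only |
|---|---|---|---|
| 0 | 5.0% | 6.6% | 1.6% |
| 0.34 mm (largest gap) | 48.5% | 53.7% | 5.2% |
| 0.5 mm (planned) | 80.7% | 84.2% | 3.5% |

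**5. The unnamed visit.** The plan does not say that both visits are tested. If a result at either were allowed to count, with the correlation between the two changes assumed to lie from 0.8 down to 0.3, error is about 7.9–9.5% for the t-test alone. It is about 10.3–12.5% if either method also counts (1,000,000 simulated trials per correlation).

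**6. Missing sites.** With 15% of patients assumed to lack one MBL site, simulated error is 7.0% for the GEE and 5.4% for the t-test (2,500 trials, Monte Carlo SE 0.5 points).

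**7. Secondary outcomes, six sites per implant.** A Gaussian GEE with complete data has the same 6.6%. For BOP with a binomial GEE, error is 5.8–8.5% over assumed bleeding at 10–40% of sites and within-patient correlation 0.1–0.5. At 10% bleeding with correlation 0.5, 2.7% of simulated trials gave no estimable effect.

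**8. What a correction does at 17 per arm.**
- t reference alone: 5.7%. Unbiased variance with a normal reference: 5.9%. Both parts are needed.
- Kauermann-Carroll variance with t₃₂: 5.0%, identical to the t-test; width 2.037/1.901 = 1.071 times the uncorrected.
- Mancl-DeRouen with t₃₂: 4.4%; width (17/16) × 2.037/1.960 = 1.104 times.
- BOP with a corrected variance, same assumed range: about 4.2–6.6%.

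**The case against.** The best defence is that the intent can be inferred. The sample size rests on a t-test with one measurement per patient, the t-test is listed first, and both the title and the inclusion criteria refer to 12 months. Read together, these point to a patient-mean t-test at T2. The statistician is also blinded to group, and section 7 provides for a blind data review before analysis, which limits data-driven choice.

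This makes the likely intent clearer, but it designates nothing. The operative sentence in section 4 gives both methods equal standing, a title does not choose between visits, and section 7 does not say that the blind review fixes the primary analysis.

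The 6.6% can also be challenged. It depends on software choices the plan does not state, and a GEE fitted to the T0, T1 and T2 values, rather than to change scores, need not reproduce the t-test's estimate. That is right: the figure is conditional and the excess of 1.6 points is modest. The two-visit and BOP figures likewise rest on assumed correlations and bleeding rates. They show the size of the exposure and do not predict this trial's error rate. If the plan meant that both methods must agree at one named visit, error would be 5.0% under the same conditions, but it does not say so.

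Finally, once the t-test alone is confirmatory, the GEE variance no longer affects the primary error rate. It still matters for the coverage of the reported GEE intervals and for the secondary outcomes.

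**Conclusion.** The concern holds. The omission is certain from the text: two MBL analyses, neither ranked, and no deciding visit. Its cost from the choice of method alone is modest: 6.6% error rather than 5%, and 93.4% coverage rather than 95%, given an uncorrected sandwich with a normal reference, complete balanced change scores and 17 per arm. The unnamed visit is the larger exposure, but only if a result at either visit could be claimed. With power of 80.7%, borderline results are plausible, so a cheap correction before unblinding is worth making. The sample size itself is sound.

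**What to change.** In section 4 and Study Outcomes, state that the single confirmatory analysis is the two-sided independent-samples t-test on patient-mean MBL change from T0 to T2 (12 months) at 5%. With 34 evaluable patients it has 80.7% power under the plan's assumptions, so no extra patients are needed. State that the GEE and the 6-month result are supportive and cannot overturn it.

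For every GEE, name the variance estimator and reference: a small-sample-corrected sandwich, for example Kauermann-Carroll, with a t distribution whose degrees of freedom are based on the number of patients. With complete balanced MBL data this reproduces the t-test, so the GEE adds information only when sites or visits are missing. Label GEE results for BOP as approximate.

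The cost is a few sentences of SAP text and a software setting. MBL GEE intervals become about 7% wider than uncorrected ones with Kauermann-Carroll, or about 10% with the slightly conservative Mancl-DeRouen, and no confirmatory claim can be made at 6 months.

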5. MONITORING AND AUDIT

Study Monitoring

The study will be monitored by the Principal Investigator at periodic intervals during the course of the study to ensure that the study is being conducted according to Good Clinical Practice.

The Investigators will be contacted by the PI on a regular basis. On this occasion, the progress of the study will be discussed with the Investigator and the CRFs will be checked for completeness and consistency and to verify compliance with the study protocol.

6. SUBJECT TERMINATION/WITHDRAWAL PROCEDURES

All efforts will be made to determine the reason(s) why a patient is withdrawn from the study. Subjects could be withdrawn from the study if any of the following occur:

1. Subject fails to substantially comply with the protocol requirements;
2. Subject develops a serious adverse reaction. The Study Investigator will immediately notify the PI and information will be recorded on a Serious Adverse Event Form (Appendix 3);
3. Subject elects to terminate participation in the study. Participation in the study is voluntary. A subject has the right to withdraw from the study at any time for any reason.

The Investigator may terminate the study at any time if the risk-benefit ratio is no longer favourable. Before discontinuation, the Investigator should inform the PI and ask for advice. If the Investigator is concerned about continuation of the study, his/her concerns should be transmitted immediately to the PI.

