1. STUDY DESIGN

The study design was chosen according to the current standards required by ISO, GCP and according to national requirements.

- a. A Parallel-Arm, Statistician is blinded, RCT will be established;
- b. The RCT will be run as mono-center;
- c. A total of 40 subjects will be recruited to participate in the study. It is expected that all of 34 subjects will complete the study in total;
- d. Admission into the study will be via rolling admission (estimated recruitment time: 12 months);
- e. Each subject must have posterior monoedentulia (mandibular or maxillary) intercalated;
- f. Each subject will follow the following treatment protocol:
 1. Visit 1: (Screening)
 - a. Screening and entry into study.
 - b. Verification of the eligibility of each subject by performing intraoral radiography.
 - c. Explanation of the research protocol.
 - d. Consent secured.
 - e. Delivery of the medical request for CBCT (cone beam computed tomography) and for the antibiotic (Amoxicillin 1000mg 2cp/die every 12 hours for 6 days or Azithromycin 500mg 1cp/die every 24 hours for 6 days).
 2. When CBCT is ready the patient have to give it to the Principal Investigator to confirm the eligibility of each subject and to plan the surgery. Professional dental hygiene session is performed before surgery.
 3. Visit 2: (Treatment)
 - a. Assessment of antibiotic prophylaxis, locoregional anesthesia and opening of a thickness flap limited to the intervention area.
 - b. According to the list of randomization the patient will be allocated into one of the two arm of surgical treatment. Group A (control group): placement of the endosseous crestal implant through dedicated drills with 35N insertion torque and healing abutment. Group B (test group): placement of the endosseous subcrestal implant (2 mm under crestal bone) through dedicated drills with 35N insertion

torque and GFA (Gingival Former Abutment). Both group receive the same implant: TZero® (L= 9 mm, Ø 3,6 mm or L= 7,5 mm, Ø 4,3 mm) (Advan S.r.l. [name])

- c. Suture.
- d. Execution of intra-oral and post-operative X-Rays.

After 7 days of the surgery suture removal.

- 4. Visit 3: (after 3 months from visit 2) (Treatment)
 - a. Periodontal charting around the healing abutment or GFA (PD, BOP, PI) with calibrated periodontal probe.
 - b. Impression taking for prosthetic finalization.
- 5. Visit 4: (after a week from Visit 3: Baseline – T0): (Treatment)

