- a medical report or a clinical proof does not exist;

unknown, if

- not enough information exists for evaluation

- no further contact with reporter possible.

Sound medical/clinical judgment will be applied when assessing the causality and seriousness of the adverse events.

Adverse Event Reporting

The study center will provide the study participants with emergency telephone numbers for study related support and feedback. The emergency telephone number is operated by either an investigator of the study or by a qualified person designated by the principal investigator. The schedule of reachability of the emergency telephone number will be defined prior to start of the study.

Serious Adverse Events

The Investigator shall immediately after awareness (and in any event, not later than within 24 hours after awareness) inform the PI. The Investigator will send the SAE report to the following email address: [contact]. Appendix 3 has to be used for SAE reporting. Form has to be completed electronically and in English.

Adverse Events

Adverse events will be assessed by the investigator or designee within 24 hours for severity, relationship to the study product, possible etiologies, and whether the event meets the criteria as a serious adverse event and therefore requires immediate notification to the PI. For data collection purposes, the outcome of all adverse events recorded on the Adverse Reaction section of the CRF will be designated as of the completion of the final evaluation or examination. However, the investigator is responsible for following all adverse events until resolution or until no longer of clinical concern, and providing these data to the PI. At the end of the study, the investigator will report all adverse events (serious and non-serious) to the PI on CRFs. Forms have to be completed electronically and in English.

Pregnancy

No pregnant women (according to medical history) will intentionally be enrolled in this study. In the event a woman enrolled in this clinical research study becomes pregnant during the course of the study, participation in this study will be terminated upon the clinical staff's notification of the event.

The subject's medical records used in this study will be updated to reflect the pregnancy and there will be follow- up contact until the end of the pregnancy to record the outcome in the clinical file.

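### Withdrawal for non-compliance or a serious adverse reaction is not separated from the end of outcome measurement, so 6- and 12-month MBL can be lost selectively

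*Combined protocol and SAP*

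**What the plan says.** Section 6 (Subject termination/withdrawal procedures) has one status for leaving: "Subjects could be withdrawn from the study if any of the following occur". Reason 1 is "Subject fails to substantially comply with the protocol requirements". Reason 2 is "Subject develops a serious adverse reaction". Reason 3 is the patient's own decision. The only information the section asks for at that point is the reason: "All efforts will be made to determine the reason(s) why a patient is withdrawn from the study".

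Two duties elsewhere can outlast withdrawal, and neither concerns MBL. Section 8 says that "the investigator is responsible for following all adverse events until resolution or until no longer of clinical concern", and its pregnancy paragraph keeps contact to record the outcome of the pregnancy.

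On timing, Section 1 places the randomised step at Visit 2: "According to the list of randomization the patient will be allocated into one of the two arm of surgical treatment". The outcome schedule is in Section 3 (Follow up): "Radiographically and clinical evaluation will be done at baseline (T0), 6 and 12 months (T1 and T2) in the test and control site".

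Two rules deal with patients leaving the analysis or the trial. Under Study population, "Randomized subjects who deviate from the protocol (major protocol deviation) and, for this reason, are excluded from the analysis, will be replaced". Under Concomitant Therapy in Section 2, a patient who uses prohibited therapy is excluded. Section 4 defines a safety analysis set but no efficacy set, and gives no rule for missing MBL.

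**The concern.** The randomised contrast (placement depth plus GFA or healing abutment) is set at surgery, and the primary outcome is read over the following year. A patient withdrawn in between still has the implant, or a known fate for it, and remains informative about the arm. Under Section 6 as written, nobody is asked to take that patient's later films.

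The losses need not be random. The Introduction presents bone resorption and soft-tissue infection as the problems that implant position and the device may affect, so a serious reaction at the implant could be related both to arm and to MBL. Non-compliance is not defined and could also go with a worse outcome. Withdrawal is optional, with no criteria for when to use it and no named decision-maker, in a trial where Section 2 says that the operator knows the allocation.

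Nothing later in the plan repairs this. The 15% drop-out allowance protects power, not comparability. Replacing excluded patients restores the count, not the randomised comparison. The planned t-test and GEE can use only measurements that were taken. The MBL comparison and the soft-tissue secondary outcomes are both exposed.

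**Working it through.** **Step 1. The plan's own figures.** Inputs from Section 4: SD 0.5 mm, difference 0.5 mm, 5% significance, independent-samples t-test, equal groups, 15% drop-out. The standardised effect is 0.5/0.5 = 1.0. With a two-sided test (the sidedness is not stated), 16 per arm gives 78.1% power and 17 per arm gives 80.7%, so 34 evaluable patients reproduces. Then 34/0.85 = 40, which also reproduces. The allowance is 40 − 34 = 6 patients for all causes. No figure in the plan is disputed.

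**Step 2. What a withdrawal costs, by timing** (Section 1 visit schedule):

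| Withdrawn | MBL values not provided for |
|---|---|
| Before Visit 4 | T0, 6 and 12 months |
| After Visit 4, before Visit 5 | 6 and 12 months |
| After Visit 5, before Visit 6 | 12 months only |

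**Step 3. Illustrative shift in one arm's mean.** Suppose k of 20 patients in one arm are lost, and their mean bone loss would have been D mm worse than that of the other 20 − k, whose mean is m. The full-arm mean is [(20 − k)m + k(m + D)]/20 = m + kD/20. The observed mean is m, so the arm looks better than it is by kD/20. Neither k nor D is in the documents. The ranges k = 1 to 3 and D = 0.5 to 1.5 mm are assumptions. Each cell shows the shift in mm, its share of 0.5 mm, and the two-sided rejection rate when there is truly no difference (noncentral t, SD 0.5 mm, 20 − k against 20 patients, nominal 5%).

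| k lost, one arm only | D = 0.5 mm | D = 1.0 mm | D = 1.5 mm |
|---|---|---|---|
| 1 | 0.025; 5%; 5.3% | 0.050; 10%; 6.1% | 0.075; 15%; 7.4% |
| 2 | 0.050; 10%; 6.0% | 0.100; 20%; 9.2% | 0.150; 30%; 14.6% |
| 3 | 0.075; 15%; 7.3% | 0.150; 30%; 14.3% | 0.225; 45%; 26.4% |

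**Step 4. Losses in both arms.** The net bias in the comparison is (k₁D₁ − k₂D₂)/20. With k₁ = k₂ and D₁ = D₂ it is zero. Only a difference between the arms in number or severity matters.

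**Step 5. Effect of keeping patients.** The sample size does not change. If all 40 were measured, power would be 86.9%, against 80.7% with 34. This is an upper limit, because some patients will leave by their own choice or not attend.

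**The case against.** The case for treating this as no more than a minor clarification is substantial, and several parts of it stand.

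- A reader might infer that the protocol stops measurement for every such patient. It does not say so. Withdrawal is possible rather than required, and the text is silent on later films. The gap is that nothing provides for them.
- A reader might also infer that, after Visit 2, there is no study treatment left to stop and that withdrawal therefore serves no protective purpose. The documents do not support this. The flow chart labels Visits 3 and 4 as treatment, the crown is fitted and loaded at Visit 4, and Section 4 expects some adverse events to lead to study treatment being stopped, reduced or withdrawn. Whether a patient should be withdrawn is a clinical matter outside this point.
- It is tempting to say that unblinded staff decide who leaves. Section 6 names no decision-maker, so this is a possibility only.
- Non-attendance is a separate route. The follow-up hygiene sessions fall at T1 and T2, so a patient who skips one also misses the film, whatever Section 6 says.
- The one-arm scenario is constructed. The 15% allowance covers all causes, including patient choice. Section 8 defines serious events narrowly and the participants are systemically healthy, so several withdrawals under reason 2 in one arm of 20 is not something the documents predict.

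These points limit the wording and the size. They do not supply the missing provision. Nor is this only a question of analysis population: an intention-to-treat set cannot use a film that was never taken. For reason 1, however, the exclusion rule under Study population acts as well, so the two have to be changed together.

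**Conclusion.** The point holds in a limited form. Section 6 allows withdrawal from the study under reasons 1 and 2 without saying whether outcome measurement continues, and no other section fills the gap. Outcomes can therefore be lost for reasons plausibly linked to prognosis and arm.

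The actual bias cannot be derived from the documents. Under the stated assumptions it runs from negligible (one patient, 0.025 mm, rejection rate 5.3%) to material (three patients in one arm only, 0.225 mm, rejection rate 26.4%), and it is nil if losses are balanced in number and severity. A reader might take the upper figure as an expected effect. It is the top of an assumed range and depends on losses falling in one arm only.

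The change is worth making because it is inexpensive and has to be settled before follow-up ends. It is not a reason to doubt the sample size or the design.

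**What to change.** Add a paragraph to Section 6, with matching consent wording (the consent form was not available to check). It should state that a patient withdrawn under reason 1 or 2 who still consents is asked to attend the planned T1 and T2 film and charting, and that these data are analysed in the arm as randomised.

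Reconcile this with two existing rules, since otherwise the new text would contradict them: the exclusion and replacement of major protocol deviators under Study population, and the exclusion for prohibited therapy under Concomitant Therapy in Section 2.

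Leave unchanged the patient's right to withdraw consent (Sections 6 and 11), the pregnancy rule in Section 8, and all clinical care decisions.

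The cost is a protocol amendment with the approval that Section 9 requires, and some effort to bring these patients back. The visits are already scheduled, although the documents contain no budget against which to check their cost. Some patients will still not attend, so the change reduces selective loss but does not remove it.
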